#### **Physical Functioning/Functional Capacity**

Physical Functioning/Functional Capacity will be assessed using the following assessments: Chair-Stand Test, Timed Up and Go, and 6-Minute Walk Distance outcomes as described previously. These measures will complement the exercise capacity measure.

**Chair-Stand Test:** The 5-repetition Chair-Stand Test measures the time taken to complete 5 repetitions of the sit-to-stand maneuver. All sit-to-stand maneuvers will be performed from a chair without an arm rest at 43 cm in height and 47.5 cm in depth. Standardized instructions will be provided as follows: "By the count of 3, please stand up and sit down as quickly as possible for 5 times. Place your hands on your lap, and do not use them throughout the procedure. Lean your back against the chair's backrest at the end of every repetition." **Note:** Timing will start when the subject's back left the backrest and will be stopped once the back touched the backrest.

**Timed Up and Go:** Subjects will be required to stand up from a chair with armrests, walk 3 meters (9.8 feet), turn around, return to the chair, and sit down. **Note:** The time taken to complete this task will be measured in seconds with a stopwatch.

**6-Minute Walk Test:** The 6-minute Walk Test will be conducted according to the guidelines of the American Thoracic Society (ATS) to determine the 6MWD. Subjects will be instructed to cover the longest distance possible in 6 minutes under the supervision of an exercise physiologist or trained designee. The walked distance will be determined in a measured corridor between 2 cones that were placed 30 meters apart. Age- and sex-predicted 6MWD will be calculated from the equation of Gibbons et al.

#### **Patient-Reported Outcomes**

Data on patient-reported changes in fatigue will be collected using the Functional Assessment in Chronic Illness Therapy – Fatigue Questionnaire (**FACIT-F**) that can be found in **Appendix B**. Data on kidney cancer symptoms will be collected using the Functional Assessment of Cancer Therapy-Kidney Symptom Index-19 (**FKSI-19**) that can be found in **Appendix C**. Data on leisure time exercise habits will be collected using the 4-item **Godin Leisure Time Exercise Questionnaire** that can be found in **Appendix D**. Data on depression will be collected using the Hospital Anxiety and Depression Survey (HADS) that can be found in **Appendix E**.

#### **Plasma Angiome Multiplex ELISA**

##### **PROCESSING INSTRUCTIONS:**

Biomarker assays are time sensitive. Samples must be processed within one hour of collection.

For plasma samples:

1. Draw one 10ml lavender top (K2EDTA) tube (BD Vacutainer, Catalog no. 366643). Please fill the tube completely.
2. Invert tubes 10 times to mix blood
3. Centrifuge at 4°C at 2500 x g for 15 minutes (or in accordance with centrifuge manufacturer's instructions)
4. Remove plasma from tube and transfer equally into two separate clean 15ml polypropylene tubes
5. Repeat centrifuge at 4°C at 2500 x g for 15 minutes (or in accordance with centrifuge manufacturer's instructions)
6. Aliquot approximately 1.0ml of plasma from each tube into each 2.0 ml pink capped cryovial. Total of 5 pink capped cryovials needed for EDTA plasma.
7. Label and freeze at -80°C\* (see labeling instructions below)

LABELING INSTRUCTIONS:

Plasma-containing tubes need to be labeled with the following information (label template to be sent electronically):

1. Protocol Name
2. Subject Study Number
3. Subject Initials
4. Sample Date and Time
5. Sample Type (ie. EDTA plasma)

**Step Counts and Blood Pressure Monitoring (both optional; up to N=16)**

- Subjects in this portion of the study must have Bluetooth-enabled smart phone.
- Each subject who elects to participate in this optional assessment will be provided a Garmin wrist-worn accelerometer and will be taught to download the Garmin smart phone application.
- Subjects will also be provided an iHealth BP cuff that will allow the patient to monitor his or her BP.
- Each subject will be taught by a trained staff member regarding general use of the activity tracker (Garmin Ltd) and wireless BP cuff (iHealth, Inc) to monitor the patient's step and blood pressure respectively. Both the activity monitor and wireless BP cuff are commercially available devices, with easy-to-use instruction manuals. The patient will need to set up an SGHlx account (web-based software platform, developed and managed by Promantus Inc., which will securely transmit device data to the investigator; <http://sghlx.org>). A trained staff member will help the patient set up this account, which will allow the patient to send their activity tracker and blood pressure data electronically directly to the investigators.
- The patients will be recommended to monitor their activity and blood pressure on a daily basis, but the patient will have full autonomy regarding usage of these devices as well as the data they will wish to share with the investigators through the online data transferring website SGHlx.
- All patient health data from SGHlx will be downloaded by the investigators or study personnel and transferred to the study's Medidata RAVE database.

## 9 SAFETY MONITORING AND REPORTING

The PI is responsible for the identification and documentation of adverse events (AEs) and serious adverse events (SAEs). At each study visit, the PI or trained designee must assess, through non-suggestive inquiries of the subject or evaluation of study assessments, whether an AE or SAE has occurred.

## 9.1 Adverse Events (AEs)

An adverse event (AE) is any untoward medical occurrence in a subject receiving study drug and that does not necessarily have a causal relationship with this treatment. For this protocol, the definition of AE also includes worsening of any pre-existing medical condition. An AE can therefore be any unfavorable and unintended or worsening sign (including an abnormal laboratory finding), symptom, or disease temporally associated with the use of sunitinib, whether or not related to use of the sunitinib. Abnormal laboratory findings without clinical significance (based on the PI's judgment) should not be recorded as AEs. **Note:** Laboratory value changes that require therapy or adjustment in prior therapy are considered adverse events.

All non-serious adverse events will be collected from the time of first dose of study drug until the End of Treatment Visit. Serious adverse events that are related to study procedures are recorded from the time the informed consent form is signed until the End of Treatment Visit (or screen failure). These AEs must be recorded in the subject's medical record and adverse events case report form.

AEs will be assessed according to the Common Terminology Criteria for Adverse Events (CTCAE), version 4.0. If CTCAE grading does not exist for an AE, the severity of the AE will be graded as mild (1), moderate (2), severe (3), life-threatening (4), or fatal (5).

Attribution of AEs will be indicated as follows:

- Definite: The AE is clearly related to the study drug or exercise testing.
- Probably: The AE is likely related to the study drug or exercise testing.
- Possible: The AE may be related to the study drug or exercise testing.
- Unlikely: The AE is doubtfully related to the study drug or exercise testing.
- Unrelated: The AE is clearly NOT related to the study drug or exercise testing.

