Exploratory	To evaluate safety and tolerability of both: (a) Sunitinib and (b) Exercise testing	Eligibility rate, attrition rate, and adverse event rate (CTCAE v4.0) in each arm	See Section 11.5
Exploratory	To determine the dose intensity of sunitinib	Patient- reported drug diaries	See Section 11.5
Exploratory	To estimate early change in VO 2 peak at 4-5 weeks compared with baseline	Change in VO 2 peak from baseline to 4-5 weeks	See Section 11.5
Exploratory	To collect plasma angiome samples for analysis and correlation with primary and key secondary endpoints	Plasma angiome multiplex ELISA	See Section 11.5
Exploratory	To use real-time electronic monitoring to describe the following over the study period (subset of patients): 
 
(a) Changes in daily physical activity
 
(b) Changes in daily blood pressure
 
	
 
(a) Steps per day
 
(b) Daily blood pressure (mmHg) reading
 
	See Section 11.5

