## 8.1 Screening Examination

The screening examination will take place between Day -84 and -1. The subject must sign an Informed Consent before any screening procedure takes place. Subject data to be collected at the Screening Examination includes:

- Informed Consent
- Eligibility Criteria
- Medical History
- Physical Exam
- Height, Weight, BMI
- Vital Signs
- Performance Status (KPS)
- Concomitant Medications
- Adverse Events (baseline symptoms)

- CBC with Platelets (hemoglobin, hematocrit, platelet count, white blood cell count, total [absolute] neutrophils)
- Serum Chemistry (sodium, potassium, chloride, total CO2 [bicarbonate], calcium, BUN, creatinine, glucose, albumin, total bilirubin, total protein, alkaline phosphatase, AST, ALT)
- Thyroid function (TSH and free T4)
- UPC (see **Appendix G**)
- Serum pregnancy test
- Echo
- CT chest, abdomen, and pelvis
- Bone scan (optional; if subject has known bone metastases then bone scan is required)

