## 8.2 Exercise Testing Days A and B

An informed consent must be signed by the subject before any screening procedure takes place. Baseline exercise testing will take place between Day -28 and -1, over approximately 2 days (CPET and Muscular Strength must be at least 24 hours apart). Subject data to be collected at Baseline Exercise Testing includes:

Examination and procedures include:

- Physical Exam
- Weight, BMI

- Vital Signs
- Performance Status (KPS)
- Concomitant Medications
- Adverse Events (SAE's)
- CBC with Platelets (hemoglobin, hematocrit, platelet count, white blood cell count, total [absolute] neutrophils)
- Serum Chemistry (sodium, potassium, chloride, total CO2 [bicarbonate], calcium, BUN, creatinine, glucose, albumin, total bilirubin, total protein, alkaline phosphatase, AST, ALT)
- UPC (see **Appendix G**)
- CPET
- Rest and exercise 2-D and 3-D echocardiography
- Muscular Strength (must be at least 24 hours before or after CPET to allow for adequate recovery)
- Muscular Endurance (must be at least 24 hours before or after CPET to allow for adequate recovery)
- Muscle CSA (CT)
- Chair Stand
- Timed Up and Go
- 6 Minute Walk Distance
- FACIT-Fatigue
- FCSI-19
- Godin Leisure Time Exercise Questionnaire
- HADS
- Plasma angiome multiplex ELISA
- Step counts (give device to subject, optional)
- Blood pressure (give device to subject, optional)

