### 8.3 Randomization

Subjects will be randomized after inclusion/exclusion criteria are met, exercise testing is complete and subject has completed an acceptable CPET and Muscular Strength. Exercise Testing Day B and Randomization may occur on the same day if eligibility is confirmed prior to randomization. Randomization and related activities can occur between days -28 to -1.

### 8.4 Treatment Period: Day 1

Day 1 is defined as the day on which the subject begins taking sunitinib.

**Note:** Subjects should start treatment with sunitinib according to the schedule to which they are randomized.

Examinations include:

- Physical Exam
- Weight, BMI
- Vital Signs
- Performance Status (KPS)
- Concomitant Medications
- Adverse Events
- CBC with Platelets (hemoglobin, hematocrit, platelet count, white blood cell count, total [absolute] neutrophils)
- Serum Chemistry (sodium, potassium, chloride, total CO2 [bicarbonate], calcium, BUN, creatinine, glucose, albumin, total bilirubin, total protein, alkaline phosphatase, AST, ALT)
- UPC (see **Appendix G**)
- Note: Many of these activities do not need to be repeated if they are performed within 14 days of day 1 (see **Schedule of Events**).
- Drug diary (give to subject)

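### Non-serious adverse events from the baseline exercise tests are not collected, so the exploratory exercise-testing safety objective has no pre-drug reference for them

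*Combined protocol and SAP*

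**What the plan says.** The exploratory objective in section 4 is "To evaluate safety and tolerability of both: (a) Sunitinib and (b) Exercise testing". Its endpoint includes a CTCAE-graded adverse event rate in each arm.

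The collection rule is in section 9.1 and again in footnote h of Table 3: "All non-serious adverse events will be collected from the time of first dose of study drug until the End of Treatment Visit". The next sentence sets a wider window for one class of event: "Serious adverse events that are related to study procedures are recorded from the time the informed consent form is signed", up to the End of Treatment Visit or screen failure. Section 9.1 also defines an adverse event as "any untoward medical occurrence in a subject receiving study drug", and its attribution scale asks in one step whether an event is related to the drug or to exercise testing.

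On timing, section 8.2 says "Baseline exercise testing will take place between Day -28 and -1, over approximately 2 days", and section 8.4 says "Day 1 is defined as the day on which the subject begins taking sunitinib". The adverse event entry for the baseline exercise visits in section 8.2 is "Adverse Events (SAE's", that is, serious events only. The screening entry in section 8.1 is "Adverse Events (baseline symptoms".

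Two other places read more broadly. The opening of section 9 has staff assess adverse events at every study visit, and Table 3 marks the Adverse Events row at Exercise Testing A and B. The restriction appears only in footnote h, section 8.2 and section 9.1.

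**The concern.** Section 9.1.2 names what CPET is expected to cause: fatigue, sore muscles, joint and back pain, and cramps. It lists these apart from the rare serious effects, so they would usually be non-serious. At baseline, the excluded class of event is therefore the one the protocol expects from testing.

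The baseline tests are also the only ones done before any sunitinib. Fatigue is an expected effect of CPET (section 9.1.2), a common reaction to sunitinib (section 3.2) and an event of special interest whose attribution must be noted throughout (section 9.1.1). If non-serious events are kept only after the drug has started, and the attribution scale does not separate drug from test, the data offer no way to tell the two sources apart. Section 3.3 says that fatigue in this setting needs to be better understood and that later studies will include exercise training. A clean description of how patients tolerate maximal testing before drug would serve that purpose.

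**Working it through.** The plan states no figure on this point, so there is none to reproduce. The check compares the collection windows with the test schedule and then counts tests.

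**Windows against the schedule**

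| Item | Baseline tests (Day -28 to -1) | Day 29/36 and Day 85 tests |
|---|---|---|
| Non-serious events (9.1, footnote h) | outside the window | inside |
| Procedure-related serious events (9.1, footnote h) | inside, from consent | inside |
| Visit checklist (8.2; 8.5, 8.6) | serious events only | adverse events |

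Sections 9.1 and 8.2 and footnote h agree, so this is a stated rule and not a slip in one place.

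**Scheduled tests per completing patient**

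- CPET (Table 3): Exercise Testing A, Day 29/36, Day 85. One of three precedes the first dose.
- Rest and exercise echocardiography (Table 3): Exercise Testing A, Day 85. One of two.
- Strength and endurance: Exercise Testing B, Day 29/36, Day 85 by Table 3, so one of three. Section 8.5 omits it at Day 29/36, which gives one of two. The two places need reconciling.

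**Share of tests outside the window**

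With k later time points and a fraction c of patients completing each one, the share is 1 / (1 + k × c).

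- Full completion, k = 2: 1/3 = 33%. k = 1: 1/2 = 50%.
- c = 0.8 at every later visit (my assumption, taken from the 20% dropout in section 11.6), k = 2: 1/2.6 = 38%. k = 1: 1/1.8 = 56%.

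With the 36 accrued patients of section 11.6 and full completion, 36 of 36 × 3 = 108 CPETs fall outside the window. Baseline CPETs in patients who then fail screening would add to the uncollected tests; the documents give no number for them.

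**What this does to a rate**

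Suppose every test carries the same probability p of a non-serious event.

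- With all 108 CPETs observed, the expected count is 108p. With 72 observed it is 72p, a loss of 36/108 = one third.
- The rate per observed test is 72p/72 = p in expectation, so it is not biased.
- If tests are treated as independent, the standard error of that rate grows by √(108/72) = √1.5 = 1.22. Correlation within a patient would make the factor smaller.

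The comparison of pre-dose with post-dose tests cannot be made at all, because the pre-dose numerator is not collected.

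**The case against.** The strongest reply is that the gap is narrow and the endpoint modest. The objective is exploratory in a pilot study. Section 11.5 plans only a descriptive display of adverse events by body system and preferred term for each arm, with no per-test or exercise-only rate. Baseline tests precede randomization (section 8.3), so their events could not inform a difference between schedules. All of this stands, and it limits the weight of the point.

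Partial safeguards exist. FACIT-Fatigue and FKSI-19 are completed at Exercise Testing A and give a pre-drug level of fatigue and pain. They ask about the past seven days in general, so they do not record what a test provoked. The broader wording at the start of section 9 and in Table 3 might lead some staff to record these events, but that would produce uneven data, not a remedy. Day 85 follows the planned rest weeks on both schedules (84 days is two cycles of 42 or four of 21), so that test is nominally off drug. It still comes after about 12 weeks of treatment and is no substitute for a test before exposure.

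Some stronger readings are tempting and are not supported:

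- A reader might infer that every event from the baseline tests is lost. Procedure-related serious events are recorded from consent.
- A reader might infer that patients who never start sunitinib contribute nothing. Their procedure-related serious events are recorded up to screen failure. Section 5.3.3 tallies reasons for screen failure and has case report forms completed for randomized patients who are not treated.
- A reader might infer that the exercise-testing event rate is understated. With equal rates per test it is not, provided the denominator is the tests observed. Understatement would need a higher rate at baseline, or a denominator that counts the baseline tests, and the documents give neither.

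**Conclusion.** The point holds for non-serious events only. By the plan's own rule, those arising from the baseline CPET, stress echocardiogram and strength tests are not collected. For that class of event, the exercise-testing safety objective rests entirely on tests done after sunitinib has started.

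The excluded share per completing patient is one third of CPETs, half of stress echocardiograms, and one third or one half of strength sessions, depending on whether Table 3 or section 8.5 is followed. Under the 80% completion assumption these become 38%, 56%, and 38% or 56%. The shares count tests. They translate into shares of events only if the event rate is the same at every visit, which the documents do not establish.

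The loss is in the number of events, the precision, and the pre-drug comparison. The primary VO2peak analysis and the arm comparisons are unaffected. This is a cheap improvement to an exploratory objective, not a threat to the trial's main result. It is worth making before enrolment, because events not recorded at baseline cannot be recovered reliably later.

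**What to change.** 1. In section 9.1, footnote h and section 8.2, collect non-serious events related to study procedures from the start of the first baseline exercise test, and all other non-serious events from the first dose. Leave the window for procedure-related serious events as it is.
2. Extend the adverse event definition in section 9.1 to patients undergoing study exercise testing before they receive drug. Otherwise the events in step 1 do not meet the definition.
3. Record attribution to sunitinib and to exercise testing as two separate items. Without this, post-dose events cannot be assigned to testing and the pre-dose comparison has nothing to be set against.
4. In section 11.5, report exercise-testing events per test and per patient tested, split into pre-dose and post-dose tests. State whether patients tested at baseline but not randomized are counted, since section 5.3.3 limits their data to demographics and the reason for failure.
5. Reconcile Table 3 with section 8.5 on strength testing at Day 29/36, so that the number of tests is known.

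The cost is a few edits to the text, an adverse event form opened at the first baseline exercise visit with one added attribution field, and slight extra data entry. No treatment, visit or test changes.

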### 5.3.3 Randomization

When the subject has been registered, has completed screening, and has been found eligible post-baseline testing, the study coordinator will request the subject's random assignment to one of the two treatment arms from the Medidata RAVE database.

For this pilot study, subjects will be randomly assigned (randomized) with equal probability to either sunitinib schedule 4/2 or 2/1. This study is open label, meaning that neither subjects nor study personnel will be blinded to treatment assignment.

**Note:** For subjects who are not eligible and fail the screening process, no further action is necessary and no additional information will be collected. However, the number of screen failures and reason for screen failure will be collected and tallied at the end of the study.

Case report forms will only be completed for those registered and randomized subjects, including those who do not receive treatment. However, subjects who do not receive the assigned treatment will be replaced and not counted toward the overall study sample size. Data limited to demographics and reason for screen failure will be collected for screen failures.

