- b. Informed consent may be performed within 84 days prior to enrollment (Day 1), but it must be obtained prior to the performance of any study-specific procedures.
- c. Randomization should be performed after baseline testing (specifically, CPET) is completed from day -28 to -1, but only after eligibility is confirmed. Note that the Baseline Exercise Testing Visits are structured to take place over 1-2 consecutive days. **See also footnote d. below.**
- d. Day 1 is defined as the day the patient begins taking sunitinib. Because day 1 is defined by this activity, there is no window. The day 1 Physical Exam, Weight, BMI, Vital Signs, PS, Con Meds, AEs, and labs have a  $\pm 3$  day window.
- e. A complete physical examination is required at the Screening, Exercise Testing Day A, Day 29-36, and Day 85 visits. A brief symptom-directed physical examination should be performed at all other clinic visits.
- f. Vital signs (temperature, blood pressure, heart rate) are to be obtained at each visit. SpO2 collected at baseline.
- g. Performance status measured by KPS (as part of IDMC) (see **Appendix A**) at screening. KPS will be used throughout the remainder of the study.
- h. All non-serious adverse events will be collected from the time of first dose of study drug until the End of Treatment Visit. Serious adverse events that are related to study procedures are recorded from the time the informed consent form is signed until the End of Treatment Visit (or screen failure). In the event of no End of Treatment Visit, adverse event information will be collected through 30 days after the last dose of study drug. Subjects should be contacted by phone for adverse event follow-up if they do not come to the clinic for the End of Treatment Visit.
- i. Clinical laboratory tests may be performed at unscheduled visits if clinically indicated.
- j. Thyroid function tests (TFTs) should include TSH and free T4.
- k. If UPC  $\geq 1$  (see **Appendix G**) at the baseline/ screening assessment, then a 24-hour urine protein must be assessed. Subjects must have a 24-hour urine protein value  $< 1$  g to be eligible.

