## 9.2 Serious Adverse Events (SAEs)

An AE is considered “serious” if in the opinion of the investigator it is one of the following outcomes:

- Fatal
- Life threatening
- Constitutes a congenital anomaly or birth defect
- A medically significant condition (defined as an event that compromises subject safety or may require medical or surgical intervention to prevent one of the three outcomes above).
- Requires inpatient hospitalization or prolongation of existing hospitalization
- Results in persistent or significant incapacity or substantial disruption to conduct normal life functions

SAE reporting criteria defined below

**A. Subset of SAEs Reportable for this Study.** Because the Pfizer Product used in this Study is a mature marketed product with a well-established safety profile, only SAEs that fit into any of the following categories need to be reported to Pfizer: (1) a death, regardless of whether it is considered related to treatment with the Pfizer Product, (2) a non-fatal SAE that occurs during the reporting period and that is assessed by the Principal Investigator as both related to treatment with the Pfizer Product and unexpected for that Product, (3) an SAE assessed by the Principal Investigator as related to the Pfizer Product that occurs after the SAE reporting period, or (4) an otherwise reportable event as described in paragraph B., below. An event should be considered "related" to the Pfizer Product if a relationship is at least a reasonable possibility, and "unexpectedness" should be based upon a single safety reference document identified by the Principal Investigator and documented in association with the study.

**B. Exposure During Pregnancy, Exposure During Lactation, Occupational Exposure, and Lack Of Effect.** Even though there may not be an associated SAE, exposure to the Pfizer Product during pregnancy, exposure to the Pfizer Product during lactation, and occupational exposure to the Pfizer Product are reportable, and lack of effect of the Pfizer Product may also be reportable.

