### 9.2.1 Reporting of SAEs

Serious adverse events, whether or not considered drug related, should be reported within 24 hours of becoming aware of the event, using the provided DCI SAE Report Form and the SAE Report Review Form (Site Assessment). These documents should be sent to:

- The DCI Safety Desk – [contact]; [contact]; email: [[contact]](mailto:[contact])

**Note:** If the DCI Safety Desk cannot be reached within 24 hours, the Principal Investigator should be contacted:

- [name], [contact]; [contact]; email: [[contact]](mailto:[contact])

The initial report for each SAE or death should include at minimum the following information:

- Protocol # and title
- Patient initials, study identification number, sex, age
- Date the event occurred
- Description of the SAE
- Dose level and cycle number at the time the SAE occurred
- Description of the patient's condition
- Indication whether the patient remains on study

- Causality

Follow-up information including severity, action taken, concomitant medications, and outcome should be communicated to Duke as soon as possible.

Upon receipt of the DCI SAE Report form by the DCI Safety Desk, the PI will be notified and be required to complete the PI assessment of the DCI SAE Report Review Form. The DCI Safety Desk will, in turn, report the event to Pfizer if the SAE is felt to be at least possibly related to sunitinib using the DCI SAE Report Form. The *Reportable Event Fax Cover Sheet* provided by Pfizer must also be included with each SAE submitted.

The SAE documentation, including the DCI SAE Report Form and available source records, should be faxed to Pfizer per the instructions on the SAE cover sheet.

The following minimum information is required for this documentation and report:

- Study number/IIT regulatory identifier
- Subject number, sex, and age
- Report date
- SAE description (event, seriousness of the event)
- Causal relationship to the study drug

Follow-up information for the event should be sent promptly (within 7 days) as necessary.

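### Section 9.1 and Table 3 footnote h give no case report form instruction or collection window for serious adverse events unrelated to study procedures, so the per-arm rates in 11.5 could omit serious drug toxicity

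*Combined protocol and SAP*

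**What the plan says.** Section 9.1 sets the collection rule in two sentences. The first is: "All non-serious adverse events will be collected from the time of first dose of study drug until the End of Treatment Visit". The second is: "Serious adverse events that are related to study procedures are recorded from the time the informed consent form is signed", running to the End of Treatment Visit or screen failure. It then directs: "These AEs must be recorded in the subject's medical record and adverse events case report form". Footnote h of Table 3 repeats the limit on serious events ("Serious adverse events that are related to study procedures are recorded from the time the informed consent form is signed until the End of Treatment") and adds that, where there is no such visit, "adverse event information will be collected through 30 days after the last dose of study drug".

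Section 9.2.1 governs expedited reporting and is wider: "Serious adverse events, whether or not considered drug related, should be reported within 24 hours of becoming aware of the event". It uses the institute's own SAE report form, sent to its safety desk. Section 10.2.2 makes the electronic case report form the study's main data collection document.

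Section 11.5 promises CTCAE rates for each arm by body system and preferred term. It does not name the data source and does not exclude serious events. Section 4 lists these rates under an exploratory objective on the safety of sunitinib and of exercise testing.

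On who gets a form, section 5.3.3 says: "Case report forms will only be completed for those registered and randomized subjects, including those who do not receive treatment". For screen failures it keeps only demographic data and the reason for failure.

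**The concern.** The two collection sentences do not cover every event. A serious event is covered only if a study procedure caused it. A hospitalisation for sunitinib toxicity, or a death from the cancer, is neither non-serious nor procedure-related. A site that applied the rule exactly would leave it off the form, and two study staff reading the rule differently would build different datasets.

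The per-arm rates are the stated endpoint for sunitinib safety, and section 3.3 gives better tolerability of schedule 2/1 as the overall hypothesis that this pilot is meant to help a later trial test. Tables that left out some or all serious drug toxicity would inform that trial poorly.

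A second mismatch sits beside the first. Section 9.1 records procedure-related serious events up to screen failure, but 5.3.3 provides no case report form for anyone not randomised. The baseline exercise test comes before randomisation, so this case can arise.

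**Working it through.** There is no stated figure to reproduce. The check is a comparison of texts, with an illustration of scale.

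**1. Where each type of event goes**

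| Event | 9.1 and footnote h | 9.2.1 |
|---|---|---|
| Non-serious, any grade or cause, after first dose | AE form, to End of Treatment Visit | not applicable |
| Serious, related to a study procedure | AE form, from consent | safety desk form |
| Serious, related to sunitinib | no instruction, no window | safety desk form |
| Serious, due to the cancer or another cause | no instruction, no window | safety desk form |

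The last two rows are the gap.

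**2. Conflict inside 9.1.** The same section defines an adverse event without regard to seriousness or cause, provides grades up to fatal (5), and asks for attribution to the drug or to exercise testing. A drug attribution scale and a fatal grade have little use for serious events if only procedure-related ones are entered.

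**3. Whether other text closes the gap**
- The opening of section 9 makes the investigator document both adverse and serious adverse events, but names no form and no window.
- The 30-day fallback in footnote h has no limit by seriousness or cause, but applies only when there is no End of Treatment Visit.
- Section 9.2.1 covers all serious events, but on a separate form. No visible text says that those forms are entered in, or reconciled with, the electronic case report form.
- Section 11.1 defines a safety population, not a source of events.

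None of these sends a sunitinib-related serious event to the adverse event form.

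**4. Scale, under an assumed risk.** The documents give no serious-event rate. Let p be the assumed chance that a patient has at least one serious event unrelated to a study procedure during the study period, and n the patients per arm: 15 evaluable, or 36/2 = 18 accrued (section 11.6). The expected number is n × p. The chance of at least one affected patient in an arm is 1 − (1 − p)^n.

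| p (assumed) | Expected, n = 15 | At least one, n = 15 | At least one, n = 18 |
|---|---|---|---|
| 5% | 0.75 | 1 − 0.95^15 = 54% | 60% |
| 10% | 1.5 | 1 − 0.90^15 = 79% | 85% |
| 20% | 3.0 | 1 − 0.80^15 = 96% | 98% |
| 30% | 4.5 | 1 − 0.70^15 = 99.5% | 99.8% |

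This shows what the literal rule could cost. It does not estimate what will happen.

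**5. Screen failures.** Section 9.1 runs its recording period for procedure-related serious events to screen failure and sends them to the adverse event form. Section 5.3.3 completes no case report form for that subject. Both cannot be followed.

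**The case against.** The best case on the other side is that the intent is plain and wider than the wording. On this reading the second sentence only extends the window back to consent for procedure-related serious events, and its reference to screen failure suits a pre-dose purpose. Section 8.2 fits that: it narrows the adverse event item at baseline exercise testing to serious events, while the visit lists in 8.4 to 8.6 carry no such limit. The definition, the grading, the attribution scale and the unrestricted wording of 11.5 all point the same way.

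Nor are the events lost. The initial safety report carries the study number, dose level, cycle and causality, so arm-level counts could be rebuilt. Section 11.3 separately displays discontinuations with reasons, delays and dose reductions by arm.

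Most of this stands, and it rules out several stronger readings that a reader might infer:
- That the plan excludes serious sunitinib toxicity from the form or the rates. No sentence says so; it follows only from the literal rule.
- That the tables would hold only mild events. Seriousness is not severity: non-serious grade 3 or 4 events are recorded under the literal rule.
- That the background figures in section 3.3 (17% with grade 3/4 fatigue, 20% discontinuing for adverse events) make omitted events near certain. They measure grade and discontinuation, not seriousness over 12 weeks.
- That a serious event at a baseline exercise test has no form at all. The safety desk form is not restricted to randomised subjects; only the case report form is missing, and a non-randomised subject could not enter per-arm rates.

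What the objection does not do is supply the missing instruction. A sensible intent, inferred from neighbouring text, does not replace a collection rule that is stated twice with the same limit.

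**Conclusion.** Wrong as written, of moderate severity. The collection rule in 9.1 and footnote h omits serious events unrelated to study procedures, conflicts with its own section, and is not linked to the reporting route in 9.2.1. If it is applied literally, the per-arm rates in 11.5 could be incomplete for serious drug toxicity. The number of patients affected cannot be stated; the 0.75 to 4.5 of 15 per arm rests wholly on the assumed 5% to 30%.

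The reach is limited. The safety analysis is exploratory and descriptive, makes no formal comparison of the arms, and does not touch the primary VO2peak analysis. All serious events should still reach the safety desk.

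A reader might also infer that the period used in 9.2 paragraph A ("a non-fatal SAE that occurs during the reporting period") is undefined for drug-related events. The text available for this review contains no definition, but some text between 9.2.1 and 9.3 was not available, so that point is not pressed.

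The mismatch between 9.1 and 5.3.3 on screen failures is real but small.

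**What to change.** - **9.1 and footnote h:** state that all adverse events, serious and non-serious and whatever their cause, are recorded on the adverse event case report form from first dose to the End of Treatment Visit, or to 30 days after last dose if there is no such visit. State that serious events related to study procedures are, in addition, recorded from consent.
- **11.5:** state that the per-arm rates include serious and non-serious events, and that the safety desk reports are reconciled with the electronic case report form before database lock.
- **5.3.3:** allow an adverse event form for any consented subject with a procedure-related serious event, randomised or not.

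The cost is a few sentences in an amendment and one reconciliation step. No new visits or assessments are needed, because the serious events already have to be reported. It is best done before the lock described in 8.7, since uneven capture is harder to repair afterwards.
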